Protocol Title	Evaluation of A Marketed Silicone Hydrogel Spherical Lens Used for Monovision Correction of Presbyopia
Sponsor	JJVC, [name]
Clinical Phase	Development Phase, Phase 2
Trial Registration	This study will be registered on ClinicalTrials.gov.
Test Article(s)	Investigational Product: Over-labeled ACUVUE® OASYS with Transitions™
Wear and Replacement Schedules	
Wear Schedule: The lenses will be used on a daily reusable basis.
 
Replacement Schedule: The lenses will be worn for approximately 2 weeks. A new set of lenses will be given to the subject at Visit 3 and the lenses will also be replaced if lost or damaged.

Objectives	This study is an evaluation of the visual performance and subjective responses of ACUVUE® OASYS with Transitions™ fit as monovision.
Study Endpoints	
Primary endpoints: logMAR visual acuity scores, and CLUE vision scores
 
Other endpoints: qCSF (Site 1036 only)

Study Design	
This is a single-masked, dispensing clinical trial. A total of approximately 48 myopic and 32 hyperopic eligible subjects will be targeted to complete the study. At Visit 1, the subjects will be fit in the study lens, optimized if required and wear the study lenses for approximately 2 weeks.
 
At Visit 2, the endpoints will be measured, and the subjects will be scheduled for Visit 3 after a 7±3 day wash-out.
 
The subjects will return to Visit 3 and complete a baseline and be fit with the same lens power that was dispensed at Visit 1 (No Optimizations).
 
The subjects will return for Visit 4 after wearing the final lens pair for approximately 2 weeks. The endpoint measurements will be repeated, and the final evaluation completed.
 
The primary endpoints will be visual performance scores and

	
the CLUE vision scores.
 
See the flow chart at the end of the synopsis table for the schematic of the study visits and procedures of main observations.

Sample Size	A total of approximately 80 will be targeted to complete.
Study Duration	The study will last approximately 3 to 5 months.
Anticipated Study Population	Healthy male and female volunteers with presbyopia will be screened as per criteria outlined below. All volunteers will have baseline measurements taken to ensure eligibility. The baseline procedures will occur after informed consent has been obtained. Subjects will have medical and contact lens history recorded, baseline questionnaires completed, and refractive and anterior segment status determined.
Eligibility Criteria	
Potential subjects must satisfy all of the following criteria to be enrolled in the study
 
Inclusion Criteria after Screening
 
 1. The subject must read, understand, and sign the STATEMENT OF INFORMED CONSENT and receive a fully executed copy of the form. 2. The subject must appear able and willing to adhere to the instructions set forth in this clinical protocol. 3. The subject must be between 40 and 70 years of age at the time of screening. 4. Subjects must own a wearable pair of spectacles if required for their distance vision. 5. The subject must be an adapted monovision soft contact lens wearer in both eyes (i.e., worn lenses a minimum of 2 days per week for at least 8 hours per wear day, for 1 month of more duration). 
Inclusion Criteria after Baseline
 
 6. The subject's distance spherical equivalent refraction must be in the range of +3.50 D to -4.00 D in each eye. 7. The subject's refractive cylinder must be \leq1.00 D in each eye. 8. The subject's ADD power must be in the range of +0.75 D to +2.50 D. 9. The subject must have best corrected distance visual acuity of 20/20⁻³ or better in each eye. 
Potential subjects who meet any of the following criteria will

	
be excluded from participating in the study:
 
Exclusion Criteria after Screening
 
 1. Currently Pregnant or lactating. 2. Any active or ongoing systemic disease, autoimmune disease, or use of medication, which may interfere with contact lens wear. This may include, but not be limited to, diabetes, hyperthyroidism, recurrent herpes simplex/zoster, Sjögren's syndrome, xerophthalmia, acne rosacea, Stevens-Johnson syndrome, and immunosuppressive diseases or any infectious diseases (e.g., hepatitis, tuberculosis). 3. Use of any of the following medications within 1 week prior to enrollment: oral retinoid isotretinoin (e.g., Accutane), oral tetracyclines, oral phenothiazines (e.g., Haldol, Mellaril, Thorazine, Elavil, Pamelor, Compazine), systemic steroids.
	
 4. Any previous, or planned, ocular or intraocular surgery (e.g., radial keratotomy, PRK, LASIK, lid procedures, cataract surgery, retinal surgery, dacryocystorhinostomy, etc.). 5. Use of any ocular medication, with the exception of rewetting drops. 6. Participation in any contact lens or lens care product clinical trial within 7 days prior to study enrollment. 7. Employee or immediate family member of an employee of clinical site (e.g., Investigator, Coordinator, Technician). 8. Any known hypersensitivity or allergic reaction to OPTI-FREE® Puremoist® care cleaning solution, non-preserved rewetting drop solution or sodium fluorescein. 9. History of herpetic keratitis. 10. Entropion, ectropion, chalazia, glaucoma, history of recurrent corneal erosions. 11. A history of amblyopia, strabismus or binocular vision abnormality. 
Exclusion Criteria after Baseline
 
 12. Clinically significant (Grade 3 or 4) corneal edema, corneal vascularization, corneal staining, tarsal abnormalities or bulbar injection, or any other corneal or ocular abnormalities which would contraindicate contact lens wear. 13. Any ocular infection or inflammation. 14. Any ocular abnormality that may interfere with contact

	
lens wear.
 
15. Any active or ongoing ocular or systemic allergies that may interfere with contact lens wear.

Disallowed Medications/Interventions	Concomitant medications will be documented during screening and updated during the study. Disallowed medications and therapies are medications or therapies that contraindicate contact lens wear. See the Exclusion criteria for specific details.
Measurements and Procedures	logMAR Visual acuity, Subjective responses for vision using the CLUE questionnaire, qCSF (Site 1036 only).
Microbiology or Other Laboratory Testing	None
Study Termination	The occurrence of one or more Unanticipated Adverse Device Effect (UADE), or any SAE where relationship to study agent cannot be ruled out, will result in stopping further dispensing investigational product. In the event of a UADE or SAE, the Sponsor Medical Monitor may unmask the treatment regimen of subject(s) and may discuss this with the Principal Investigator before any further subjects are enrolled.
Ancillary Supplies/ Study-Specific Materials	OPTI-FREE® Puremoist® multi-purpose care solution, Rewetting drops, lens cases, glass vials, saline, ETDRS light cabinet, logMAR charts, and Near logMAR charts.
Principal Investigator(s) and Study Institution(s)/Site(s)	A full list of Principal Investigators, clinical sites, and institutions is kept separately from the Study Protocol and is included in the study Trial Master File.

Figure 1: Study Flowchart

COMMONLY USED ABBREVIATIONS AND DEFINITIONS OF TERMS

ADD	Plus Power Required For Near Use
ADE	Adverse Device Effect
AE	Adverse Event/Adverse Experience
BCC	Binocular Crossed Cylinder
BCVA	Best Corrected Visual Acuity
BSCVA	Best Spectacle Corrected Visual Acuity
CFR	Code of Federal Regulations
CLDEQ-8	Contact Lens Dry Eye Questionnaire-8
CLUE	Contact Lens User Experience
COAS	Complete Ophthalmic Analysis System
COM	Clinical Operations Manager
CRA	Clinical Research Associate
CRF	Case Report Form
CRO	Contract Research Organization
CT	Center Thickness
■■■■■	■■■■■
D	Diopter
DMC	Data Monitoring Committee
eCRF	Electronic Case Report Form
EDC	Electronic Data Capture
ETDRS	Early Treatment Diabetic Retinopathy Study
FDA	Food and Drug Administration
GCP	Good Clinical Practice
HIPAA	Health Insurance Portability and Accountability Act
HIV	Human Immunodeficiency Virus
IB	Investigator's Brochure
ICF	Informed Consent Form
ICH	International Council for Harmonization
IDE	Investigational Device Exemption
IEC	Independent Ethics Committee
IRB	Institutional Review Board
ISO	International Organization for Standardization
ITT	Intent-to-Treat
JJVC	Johnson & Johnson Vision, Inc.
LC	Limbus Center
LogMAR	Logarithm of Minimal Angle of Resolution
LSM	Least Square Means
MedDRA [®]	Medical Dictionary for Regulatory Activities
MOP	Manual of Procedures
NIH	National Institutes of Health
OD	Right Eye
OHRP	Office for Human Research Protections

OHSR	Office for Human Subjects Research
OS	Left Eye
OU	Both Eyes
PD	Protocol Deviation
PHI	Protected Health Information
PI	Principal Investigator
PIG	Patient Instruction Guide
PQC	Product Quality Complaint
PRO	Patient Reported Outcome
QA	Quality Assurance
QC	Quality Control
SAE	Serious Adverse Event/Serious Adverse Experience
SAP	Statistical Analysis Plan
SAS	Statistical Analysis System
SD	Standard Deviation
SOP	Standard Operating Procedure
UADE	Unanticipated Adverse Device Effect
USADE	Unanticipated Serious Adverse Device Effect
VA	Visual Acuity

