11. STUDY TERMINATION

The occurrence of one or more Unanticipated Serious Adverse Device Effect (USADE), or any SAE where the relationship to study agent cannot be ruled out, may result in stopping further dispensing of test article. In the event of a USADE or SAE, the Sponsor may unmask the treatment regimen for the subject(s) and will discuss this with the Investigator before any further subjects are enrolled.

The Sponsor will determine when a study will be stopped. The Principal Investigator always has the discretion to initiate stopping the study based on patient safety or if information indicates the study's results are compromised.

JJV reserves the right to terminate the study at any time for any reason. Additionally, the IEC/IRB reserves the right to terminate the study if an unreasonable risk is determined. The study can be terminated by the Principal Investigator at the individual clinical site due to specific clinical observations, if in their opinion, after a discussion with JJV, it is determined that it would be unwise to continue at the clinical site.

JJV (and the IEC/IRB and DMC, if applicable) will evaluate all adverse events. If it is determined that an adverse event presents an unreasonable risk, the investigation, or that part of the investigation presenting the risk, will be terminated, as soon as possible.

Should the study be terminated (either prematurely or as scheduled), the Investigator will notify the IEC/IRB and Regulatory Authority as required by local regulatory requirements.

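### After the same serious event, the synopsis makes a halt in lens dispensing automatic and Section 11 makes it discretionary; the two texts must be reconciled

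*Combined protocol and SAP*

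**What the plan says.** Two places state what happens to dispensing after a serious event.

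- **Synopsis, Study Termination.** A UADE, or an SAE not shown to be unrelated, "will result in stopping further dispensing investigational product". The sponsor's medical monitor may unmask and "may discuss this with the Principal Investigator before any further subjects are enrolled".
- **Section 11, Study Termination.** A USADE, or an SAE not shown to be unrelated, "may result in stopping further dispensing of test article". The sponsor may unmask and "will discuss this with the Investigator before any further subjects are enrolled". The section adds that the decision to stop the study lies with the sponsor.

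Section 13.1 defines UADE. USADE is spelled out in the abbreviation list and in Section 11 but has no definition in Section 13.1. Nothing in the protocol says whether the synopsis or the body text governs when they differ.

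**The concern.** A rule that fires on a named event is useful only if everyone knows beforehand what it requires. Here a reader of the synopsis expects dispensing to stop, while a reader of Section 11 expects a decision by the sponsor.

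The situation is realistic. Section 13.1 lists microbial keratitis and iritis among ocular SAEs, and the package insert in Appendix C names iritis among the possible problems of lens wear. Dispensing also runs through the whole study: a first pair at Visit 1, a second at Visit 3, and replacements for lost or damaged lenses. The rule thus bears on new enrolees and on subjects between wearing cycles.

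Three things are at stake:

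- **Exposure.** Whether further subjects receive lenses after a qualifying event depends on which text is read.
- **Oversight.** The ethics committee approves the protocol (Section 18.3), the investigator must follow the plan (Section 18.2) and monitors check conformity (Section 17). Continued dispensing would be allowed by Section 11 and a deviation from the synopsis.
- **Data.** Section 14.1 places all analyses on the per-protocol population, and Section 14.3 requires completion of all visits to enter it. A subject who receives no second pair cannot complete Visit 4 and so leaves that population, including for the 2-week primary comparison.

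**Working it through.** No arithmetic applies, so the check sets the two texts side by side.

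| Element | Synopsis | Section 11 | Agree? |
|---|---|---|---|
| Device-effect trigger | UADE | USADE | Labels differ |
| SAE trigger | SAE, relationship not excluded | SAE, relationship not excluded | Yes |
| Effect on dispensing | Will stop | May stop | **No** |
| Unmasking | Optional, by the sponsor's medical monitor | Optional, by the sponsor | Force agrees, actor differs |
| Discussion with investigator before further enrolment | May | Will | **No** |

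**Step 1: is it the same event?** For SAEs, yes. The synopsis reads "any SAE where relationship to study agent cannot be ruled out, will result in stopping further dispensing investigational product" and Section 11 reads "any SAE where the relationship to study agent cannot be ruled out, may result in stopping further dispensing of test article". The qualifier on relationship is the same, so the difference lies in the consequence.

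**Step 2: do UADE and USADE differ?** Probably not. The UADE definition in Section 13.1 is already confined to serious effects, life-threatening problems, deaths and other serious unanticipated problems. Section 13.4.1 puts the word serious in parentheses inside the UADE label. This is inconsistent terminology, and nothing indicates a second trigger.

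**Step 3: which courses of action satisfy both texts?** Take one qualifying event and read the discussion sentence as referring to the event.

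| Course | Synopsis | Section 11 |
|---|---|---|
| Stop, discuss | Met | Met |
| Stop, no discussion | Met | Not met |
| Continue, discuss | Not met | Met |
| Continue, no discussion | Not met | Not met |

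One of the four courses satisfies both. If the sentence refers only to the unmasking, and no unmasking takes place, Section 11 imposes no discussion and both stopping courses satisfy both texts. Under either reading, continuing is open under Section 11 and closed under the synopsis.

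**Step 4: does another clause settle it?** Section 11 also provides for termination once an adverse event is found to present an unreasonable risk, for the investigator to initiate stopping on safety grounds, and for the ethics committee to terminate. Section 8.2 withdraws individual subjects after certain events. The Section 11 clauses turn on a judgement about risk, and Section 8.2 concerns the affected subject. None says what happens to dispensing for everyone else when a named event occurs, and none ranks the two texts.

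**The case against.** The strongest reply is that the discrepancy is one verb in a synopsis, that Section 11 is the fuller text, and that subjects are protected in other ways. Parts of this stand, and they rule out several stronger readings.

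- **That this is the study's only safety stopping rule.** A reader might infer this from the synopsis. Section 11 contradicts it: termination for unreasonable risk is mandatory once that risk is determined, and the investigator and the ethics committee each have grounds to stop. What remains is narrower: this is the only provision found that links a halt in dispensing to a named event.
- **That a site cannot comply with both texts.** This does not follow. A permission is satisfied by acting on it, so stopping and discussing meets both. The conflict appears when Section 11's discretion is used to continue.
- **That the two texts have different triggers.** The SAE wording carries the same qualifier in both, and the UADE and USADE labels appear to mean the same thing.
- **That the discussion rule is cleanly reversed.** The sentence follows the one on unmasking, which is optional in both texts, and its referent is unclear. With one arm, one lens type and only subjects masked, the practical weight of this part is small.

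The reply does not dispose of the central point. The documents do not say that Section 11 prevails, and the other protections do not answer whether the halt is automatic.

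**Conclusion.** The contradiction is real but limited: for one class of event, the halt in dispensing is automatic in the synopsis and discretionary in Section 11. The mismatch on discussion with the investigator and the undefined USADE label are secondary and belong in the same correction.

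A single event suffices to bring it into play, and it would affect whoever among the 80 targeted completers (48 myopes and 32 hyperopes) and any replacements still had lenses to receive. Frequency cannot be estimated from the documents. No hypothesis, margin, sample size, power or type I error depends on it. The effect on the data is conditional: it arises only if a qualifying event occurs before all subjects have received their second pair.

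The conclusion assumes that both texts are in force and that no separate document ranks them. It takes no view on which rule is right. The matter should be corrected because it concerns an event-triggered safety rule and is cheap to settle in advance.

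**What to change.** Amend the synopsis and Section 11 so that both state:

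1. one consequence for dispensing after a qualifying event;
2. one rule on discussion with the investigator before further enrolment, saying whether it concerns the event or the unmasking;
3. one trigger term, defined in Section 13.1 and used throughout;
4. the same party responsible for unmasking.

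The sponsor and medical monitor decide the content of each. Alternatively, the synopsis could refer to Section 11 and restate nothing, once Section 11 holds the agreed rule.

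The cost is a wording change in a protocol amendment, with the ethics committee review that an amendment needs. It requires no extra subjects, data or analyses.

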1. INTRODUCTION AND BACKGROUND

Johnson & Johnson Vision has recently launched a new spherical contact lens, ACUVUE® OASYS with Transitions™, that has photochromic properties. The purpose of this study is to evaluate the performance of the lens when fit as monovision in a presbyopic population who habitually wear monovision correction.

1.1. Name and Descriptions of Investigational Products

Test Lens: Over-labeled ACUVUE® OASYS with Transitions™.

1.2. Intended Use of Investigational Products

The study lenses are spherical lenses intended to correct refractive ametropia (myopia or hyperopia) in subjects who may have 1.00 D or less of refractive astigmatism. The lenses are intended to be used as a 2-week, reusable, daily wear lens. The lenses require use of a care system to clean and disinfect the lenses.

1.3. Summary of Findings from Nonclinical Studies

See the ACUVUE® OASYS with Transitions™ package insert in APPENDIX C: PACKAGE INSERT (APPROVED PRODUCT).

1.4. Summary of Known Risks and Benefits to Human Subjects

See the ACUVUE® OASYS with Transitions™ package insert in APPENDIX C: PACKAGE INSERT (APPROVED PRODUCT).

1.5. Relevant Literature References and Prior Clinical Data Relevant to Proposed Clinical Study

Refer to the ACUVUE® OASYS with Transitions™ package insert in APPENDIX C: PACKAGE INSERT (APPROVED PRODUCT).

2. STUDY OBJECTIVES, ENDPOINTS AND HYPOTHESES

2.1. Objectives

This study is an evaluation of the visual performance and subjective response of ACUVUE® OASYS with Transitions™ fit as monovision.

2.2. Endpoints

The study endpoints will be the subjective CLUE Vision scores and logMAR visual acuity. Additional endpoints will be quantitative contrast sensitivity function (qCSF) measured at site 1036.

Primary Endpoint

- logMAR visual acuity scores, and CLUE vision scores

Secondary Endpoint

- N/A

Other Observations

- qCSF (Site 1036 only)

2.3. Hypotheses

The following primary hypotheses will be tested throughout this investigation.

Primary Hypotheses:

1. After 10 to 14 days of wear, the distance, binocular, high luminance, high contrast visual acuity score for the Test lens will be statistically better than +0.01 logMAR.
2. After 10 to 14 days of wear, the intermediate, binocular, high luminance, high contrast visual acuity score for the Test lens will be statistically better than +0.17 logMAR.
3. After 10 to 14 days of wear, the near, binocular, high luminance, high contrast visual acuity score for the Test lens will be statistically better than +0.17 logMAR.
4. After the first 10 to 14 days of wear, the PRO CLUE vision scores for the Test lens will be statistically better than 32 CLUE points. This will be recorded by the subject using the CLUE Follow-up Questionnaire from Visit 2.

If all the primary hypotheses are met, the following secondary hypotheses will be tested.

Secondary Hypotheses:

The PRO CLUE vision scores after the second 10 to 14 days wear cycle (Visit 4) will be statistically better than the score after the first 10 to 14 days wear cycle (Visit 2). This will be recorded using the CLUE Follow-up Questionnaire.

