14.2. Sample Size Justification

A total of 80 subjects (48 myopes and 32 hyperopes) are targeted to complete the study.

Using the POWER procedure in SAS 9.4, below is the summary of sample size required based on the different assumptions of the true LogMAR visual acuity and CLUE scores. The sample size was calculated for the non-inferiority tests (using 0.05 as the margin) with at least 90% of statistical power and 2-sided type I error of 0.05. Assuming the true LogMAR visual acuity is between 0.00 to 0.05 (distance) or 0.08 to 0.12 (near), and true CLUE vision score is between 38 to 42 points.

- Binocular LogMAR visual acuity (distance)

True Value	Estimated Standard Deviation	# of subjects needed	Actual Power
0.00	0.12	18	0.915
0.02	0.12	26	0.904
0.05	0.12	63	0.902

- Binocular LogMAR visual acuity (intermediate and near)

True Value	Estimated Standard Deviation	# of subjects needed	Actual Power
0.08	0.12	21	0.905
0.10	0.12	33	0.901
0.12	0.12	63	0.902

- CLUE vision score

True Value	Estimated Standard Deviation	# of subjects needed	Actual Power
38	17	87	0.902
40	17	50	0.903
42	17	33	0.906

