14.5. Primary Analysis

Primary efficacy analysis:

Binocular, high luminance, high contrast logMAR visual acuity will be analyzed using a linear mixed model. The model will include the experimental design factors: distance (distance/intermediate/near) and time point (2 week or 4 week) as fixed effects; and site and subject nested in site as random effects. Other baseline characteristics known to be important such as age, gender, subject group (myope/hyperope), and/or ADD power will be included as fixed covariates when appropriate. The covariance between residual errors from the same subject at the same time point across distances will be selected based on the finite-sample corrected Akaike's Information Criterion.⁶ Covariance structures considered will include: Homogenous Compound Symmetry (CS), Heterogeneous Compound Symmetry (CSH), and Unstructured covariance structure (UN). The structure that returns the lowest Akaike Information Criteria Corrected (AICC) will be selected as the structure that best fit the data. Heterogeneous models across study populations and/or distance will be considered using a log-likelihood ratio test.

Comparisons will be carried out using 95% confidence intervals (CIs) constructed of Least-square means (LSM) from the linear mixed models. Statistical superiority will be concluded if the upper limit of the confidence intervals of the Test lens is below +0.10 logMAR for distance, and below +0.17 logMAR for intermediate and near.

CLUE Vision

Overall quality of vision scores will be analyzed using a linear mixed model adjusting for baseline values as fixed covariates. The model will include the experimental design factors: time point (2 week or 4 week) as the fixed effect; and site and subject nested in site as random effects. Other baseline characteristics known to be important such as age, gender, subject group (myope/hyperope), and/or ADD power will be included as fixed covariates when appropriate. The covariance between residual errors from the same subject across lens wearing periods/time point will be selected based on the finite-sample corrected Akaike's Information Criterion.⁶ Covariance structures considered may include: Homogenous compound symmetry (CS) and Unstructured covariance structure (UN). The structure that returns the lowest Akaike Information Criteria Corrected (AICC) will be selected as the structure that best fit the data.

Primary Hypothesis:

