14.10. Procedure for Reporting Deviations from Statistical Plan

The analysis will be conducted according to that specified in above sections. There are no known reasons for which it is planned to deviate from these analysis methods. If for any reason a change is made, the change will be documented in the study report along with a justification for the change.

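### The primary distance-acuity threshold is +0.01 logMAR in Section 2.3 but +0.10 logMAR in the Section 14.5 decision rule, so the same result can pass one and fail the other

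*Combined protocol and SAP*

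**What the plan says.** Section 2.3, primary hypothesis 1, concerns binocular, high-luminance acuity at distance after 10 to 14 days of wear and requires that the "high contrast visual acuity score for the Test lens will be statistically better than +0.01 logMAR".

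Section 14.5 gives the operational rule for the same endpoint. Superiority is concluded if the upper limit of the 95% confidence interval for the "Test lens is below +0.10 logMAR for distance, and below +0.17 logMAR for intermediate and near".

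The other primary thresholds are consistent. For intermediate vision, Section 2.3 says "the intermediate, binocular, high luminance, high contrast visual acuity score for the Test lens will be statistically better than +0.17 logMAR"; near vision also has +0.17, and CLUE vision has 32 points. Section 14.5 repeats all three.

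Section 14.2 does not print the distance null value. It describes the calculation this way: "The sample size was calculated for the non-inferiority tests (using 0.05 as the margin"), with at least 90% power and a two-sided type I error of 0.05. Its planning values are introduced with "Assuming the true LogMAR visual acuity is between 0.00 to 0.05 (distance) or 0.08 to 0.12 (near").

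Section 2.3 then sets a gate: "If all the primary hypotheses are met, the following secondary hypotheses will be tested". Section 14.10 says "The analysis will be conducted according to that specified in above sections", without giving any section precedence.

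**The concern.** A primary success criterion is printed with two values that differ by 0.09 logMAR. The disagreement runs one way: any result that meets +0.01 also meets +0.10, but not the reverse. A trial could therefore be reported as successful on distance acuity under Section 14.5 while failing its own stated hypothesis.

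Two things depend on which number applies. The first is the primary conclusion for distance. The second is the gate to the secondary CLUE comparison (Visit 4 against Visit 2), which opens only if every primary hypothesis is met. Meeting the distance hypothesis is necessary for that gate but not sufficient, since the other three must also be met.

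The design adds to the problem. The trial has a single arm and only subjects are masked (Sections 4.1 and 5.2), so a choice between the two numbers left until late could be made by people who have seen acuity results.

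**Working it through.** **Inputs.** Thresholds +0.01 (Section 2.3) and +0.10 (Section 14.5). From Section 14.2: SD 0.12, two-sided alpha 0.05, power at least 90%, true distance values 0.00, 0.02 and 0.05, and 80 completers. The method is a one-sample t-test with exact noncentral-t power. Success means that the upper 95% limit lies below the threshold.

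**Step 1: reproduce the Section 14.2 distance rows.** With δ = threshold − true value and noncentrality δ√n / 0.12, find the smallest n with power of at least 0.90.

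| Null value tried | True 0.00 | True 0.02 | True 0.05 |
|---|---|---|---|
| Printed in Section 14.2 | 18 (0.915) | 26 (0.904) | 63 (0.902) |
| +0.10 | 18 (0.915) | 26 (0.904) | 63 (0.902) |
| +0.01 | 1515 | none | none |
| +0.06 (= 0.01 + 0.05 margin) | 44 | 97 | 1515 |
| +0.15 (= 0.10 + 0.05 margin) | 9 | 12 | 18 |

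Only +0.10 matches, and it matches in both n and power. For +0.01, no sample size works at true values 0.02 and 0.05, because those values are already worse than the threshold. Adding the stated 0.05 margin to either threshold does not recover the table.

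**Step 2: check the method on the other endpoints.** A null of 0.17 gives 21, 33 and 63 for intermediate and near. A null of 32 (SD 17) gives 87, 50 and 33 for CLUE. Both sets match Section 14.2. So the intermediate/near and CLUE tables use the threshold printed in Section 2.3, and the distance table does not.

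**Step 3: the range of conflicting results at n = 80.**

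- Half-width = t(0.975, 79) × 0.12 / √80 = 1.990 × 0.01342 = 0.0267.
- Section 14.5 is met if the observed mean is below 0.10 − 0.0267 = +0.073.
- Section 2.3 is met if the observed mean is below 0.01 − 0.0267 = −0.017.
- Means between −0.017 and +0.073 pass Section 14.5 and fail Section 2.3. All the planning values lie inside this range.

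**Step 4: probabilities at n = 80, SD 0.12.**

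| True mean | Power against +0.10 | Power against +0.01 | Passes 14.5, fails 2.3 |
|---|---|---|---|
| 0.00 | >0.999 | 0.111 | 0.889 |
| 0.02 | >0.999 | 0.0035 | 0.996 |
| 0.05 | 0.957 | about 0 | 0.957 |

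The last column is the difference between the two before it, because meeting +0.01 implies meeting +0.10.

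**Step 5: what +0.01 would need.** With n = 80, 90% power requires δ of about 0.044, that is a true mean of about 0.01 − 0.044 = −0.034. This is outside the planning range.

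**Step 6: sensitivity to the SD.** The alternative SDs are assumptions, not values from the plan. With SD 0.08 the half-width is 0.018 and the conflict range is −0.008 to +0.082. With SD 0.15 the half-width is 0.033 and the range is −0.023 to +0.067. Both contain the whole of 0.00 to 0.05.

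**The case against.** The strongest reply is that this is a slip in one line with a clear operative rule elsewhere. Section 14.5 is the only place that says how the confidence limit is to be used, and it says +0.10. The sample-size table was built on +0.10. Two of the three planning values are worse than +0.01, so the trial cannot have been sized for it. A statistician working from Section 14 would apply +0.10, and Section 14.10 points the same way. On this view the split-verdict probabilities measure the gap between two printed numbers, not the chance that the analysis goes wrong.

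Much of this stands as evidence about which number was intended. It does not remove the conflict. Nothing in the documents says that +0.01 is an error or that Section 14.5 overrides Section 2.3, and Section 2.3 is where both the primary hypothesis and the gate are defined. A reader who checks the results against the stated hypothesis would reach the opposite verdict.

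A second reply is that the planned analysis is a mixed model using both time points, with site and subject random effects and possible covariates, so its interval may be wider or narrower than 0.0267. That is correct, and the ranges above are approximate. However, the thresholds are 0.09 apart, more than three half-widths (0.09 / 0.0267 = 3.4), so a modest change in interval width leaves the conclusion unchanged.

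**Conclusion.** The concern holds. Sections 2.3 and 14.5 give incompatible thresholds for the first primary hypothesis, and no other part of the plan reconciles them. The sample-size table identifies +0.10 as the value used in planning, so Section 2.3 is most likely where the error lies, although the documents do not say so.

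Under the plan's own assumptions a split verdict is the expected outcome, with probability 0.889 or more at each of the tabulated true values. Read as written, Section 2.3 leaves power of at most 0.111 for distance, and the secondary comparison could then hardly ever be tested. Under Section 14.5, distance power is at least 0.957. These figures rest on 80 completers, SD 0.12 and the one-sample approximation; the direction and importance of the conflict do not depend on the exact interval width.

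The non-inferiority wording and the 0.05 margin in Section 14.2 are a related but separate problem of description. They do not explain the difference.

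**What to change.** - Correct hypothesis 1 in Section 2.3 to +0.10 logMAR, in line with Section 14.5 and the value implied by Section 14.2. Record the superseded value and the reason.
- In Section 14.2, print the null value behind each set of rows (+0.10, +0.17 and 32), and explain how the 0.05 margin relates to them or remove it.
- If +0.01 is really intended, change Section 14.5 and restate the distance power figures instead. At none of the planning values do 80 subjects give 90% power against +0.01.

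Make the change before anyone reviews outcome data, and at the latest before database lock, because moving from +0.01 to +0.10 loosens a printed primary criterion in a trial where only subjects are masked.

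If +0.10 is confirmed, the cost is one corrected number and a clarifying line, with no change to procedures, enrolment or data collection. Because a primary hypothesis is altered, it should go through as a protocol amendment, with ethics committee review where Section 18.3 calls for it.
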